Aim 2: We will determine associations between SLNB and long-term outcomes, including breast cancer specific mortality, ipsilateral invasive breast cancer diagnosis, subsequent mastectomy as treated recurrence, and lasting side effects, from >9 months post-diagnosis to death or the end of this study period.

Study design

We will conduct a retrospective cohort study. Using the most up-to-date SEER-Medicare database, we will examine the impact of SLNB on clinical outcomes of women with newly diagnosed DCIS among the Medicare population. The nature of SEER-Medicare linking Medicare claims records to tumor registries participating in the NCI's SEER program allows us to select study population based on precise demographic and clinical characteristics of the patients. In our study, the population is DCIS patients older than 67 years (hereafter referred to as older women) who were enrolled in a fee-for-service Medicare program and resided in the SEER areas from 1998 to 2011 (1998-2013 for Aim 2) and who were followed up to 2012 (2015 for Aim 2).

Methodology

Our study population are generated within the SEER-Medicare linked database. To identify patients with DCIS, we will use histology and behavior codes, which are converted from the ICD-O-3 codes that tumor registries are required to report to SEER for all cases.¹⁶ Specifically, we will identify breast “cancer” patients with in situ tumor behavior (behavior code = 2). DCIS patients will be further limited to those with ICD-O-3 codes consistent with epithelial origin. We select age 67 as a cut-off value because we plan to use two years of claims data to identify patient comorbidities and to control for them in our statistical models, and data is first available at age 65.

Our Aim 1 cohort will include DCIS patients who received BCS as their first surgery (i.e. excluding patients who received mastectomy first). We expect that patients who received BCS with SLNB (compared with those who received BCS without SLNB) would be more likely to end up with mastectomy, and thus would be more likely to have side effects. Findings of the associations between SLNB and mastectomy as the final treatment for DCIS would be informative. We intend to include these patients in Aim 1 so that we can provide a comprehensive picture regarding side effects of SLNB in the context of less intensive managements.

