Our Aim 2 will examine the long-term outcomes between patients who received BCS without SLNB and patients who received BCS with SLNB. Patients who received BCS in the beginning yet ended up with mastectomy for their primary DCIS will be excluded. For patients who received BCS plus RT, SLNB will not likely provide any benefits since RT is able to control small lesions. However, we plan to determine the effects of SLNB among patients who received BCS without RT, which will have important clinical implications.

The time period for defining the cohort for the Aim 1 will be between January 1998 and December 2011. Using medical claims for this cohort, we will identify any side effects within a

9-month window (from DCIS diagnosis to 9 months post-diagnosis). The time period for defining the cohort for the Aim 2 will be from January 1998 to December 2012, and patients will be followed from 9 months after DCIS diagnosis through the latest date to which data is available in SEER-Medicare. For instance, the next SEER-Medicare linked dataset will have overall mortality through December 2015, breast cancer specific mortality through December 2013, and claims data (to identify treated recurrence) through December 2014.

We identify interventions and comparators in our study using specific international classification of Diseases, Ninth Revision, (ICD-9) codes, CPT codes and HCPCS codes. We will limit our sample to DCIS patients who received BCS as their first surgery; that is, we exclude patients whose first surgery is mastectomy, because we are only interested in patients who receive less intensive treatment and their outcomes. Because SLNB is performed by a surgeon, we identify it within a window consistent with those used in prior literature to identify breast cancer surgery, that is, between the date of the first BCS and 6 months after DCIS diagnosis. We are aware that patients may receive BCS first and mastectomy later for their primary DCIS. Furthermore, we realize that SLNB may affect whether or not patients receive mastectomy.

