Based on the input of our patient and professional advisory committee members, we propose the following outcomes of interest in this project. In Aim 1 we focus on acute/sub-acute side effects. Secondary outcomes include treatment received. In Aim 2, our primary outcomes include breast cancer specific mortality, incident ipsilateral invasive breast cancer occurrence (based on ipsilateral invasive breast cancer from SEER) and treated recurrence (based on follow-up mastectomy). Secondary outcomes include overall survival and lasting side effects. Overall survival, expected to be similar, would be used as a benchmark outcome to check performance of our model.

In addition to the key exposures (interventions and comparators) and endpoints (outcomes of interest), we will further select covariates, including patient demographics, comorbidities, tumor characteristics and prior healthcare utilization, based on prior literature and our experience. We plan to include the following covariates to control for confounding. For patient demographics, we will include patient's age, sex, ethnicity, marital status and years of diagnosis. For geographical and social-economical characteristics, we will include income, education and metropolitan residence. For patient's comorbidities, we plan to include Elixhauser comorbidity index, disability index and prior hospitalization. For DCIS characters, we will include grade, size, comedonecrosis and hormone receptor status. For health care system utilization, we will consider prior influenza vaccination, physician visit, MRI use and surgeon's volume. Last, to control for other treatment patients have received, we will adjust for mastectomy and radiation therapy.

Data management and statistical analysis

We plan to create a dataset for this project. Each patient in the SEER-Medicare dataset has a unique patient identification number. Using this information, we will be able to collect patient demographics and DCIS characteristics from the SEER registry as well as claims data from Medicare on what treatment patients have received or what side effects they have experienced. We will manage the dataset in a suitable manner that fully complies with the SEER-Medicare data use rules and confidentiality.

As a secondary data analysis, we will be unable to prevent missing data from the original dataset. We do, however, set a priori exclusion and inclusion criteria for the creation of our cohort. We

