We plan to control for selection bias using propensity score matching methodology.¹⁷ Specifically, the propensity score matching will be based on the Mahalanobis distance¹⁸ calculated using age, race, residence in a metropolitan county, comorbidity, prior influenza vaccination or prior visit to a primary care physician (both as proxies for access to care), income, preoperative MRI use, and tumor characteristics. Tumor characteristics include size, grade, comedonecrosis, and estrogen receptor status. By incorporating these factors in matching, we expect to substantially decrease bias and balance the risk for outcomes of interest between the SLNB and non-SLNB groups. We will use 2: 1 matching, as prior literature indicated that this approach results in improved precision without a commensurate increase in bias.¹⁹ To ensure robust and comprehensive matching, matches will be assigned by choosing the two best non-SLNB patient matches for each SLNB patient; when two or more SLNB patients match the same control (that is, have Mahalanobis distances minimized by the same control), one will be randomly selected as a match, and this process reiterates until all SLNB patients have two matched controls. We will assess the validity of the matching by comparing risk factors between the SLNB and non-SLNB groups using χ^2 tests. The difference in outcomes between the control and intervention groups will be estimated in a Kaplan-Meier curve. We will estimate the relative risk in the propensity score matched sample using the standard method for matched-pair data.²⁰ We will use the Cox proportional hazards models to investigate the association between various factors (grade, tumor size, and estrogen receptor status) and outcomes.²¹

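### SEER registry or region is neither matched on nor adjusted for, so regional practice can enter the SLNB estimates, chiefly for radiation and mastectomy in Aim 1

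*Combined protocol and SAP*

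**What the plan says.** The Study design section describes a data source "linking Medicare claims records to tumor registries participating in the NCI's SEER program", so the women come from more than one registry area.

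In the Methodology section, the geographic and socio-economic covariates are given in one sentence: "For geographical and social-economical characteristics, we will include income, education and metropolitan residence". Surgeon's volume is to be considered among the utilization covariates.

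In the Data management and statistical analysis section, the Mahalanobis distance is "calculated using age, race, residence in a metropolitan county, comorbidity, prior influenza vaccination or prior visit to a primary care physician", followed by "income, preoperative MRI use, and tumor characteristics". The last item is spelled out: "Tumor characteristics include size, grade, comedonecrosis, and estrogen receptor status". Metropolitan county is the only place variable.

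The same section says that the validity of the matching will be judged by comparing risk factors between the groups, that models will control for covariates left unbalanced, and that the Aim 2 models carry a shared frailty for the matched set. The planned strata are radiation, DCIS characteristics and predicted life expectancy. None is geographic.

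**The concern.** A metropolitan indicator separates urban from rural women but not one registry from another. A metropolitan SLNB patient in one area can be matched to metropolitan controls in any other.

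The opening background calls the role of SLNB in DCIS controversial, with experts on both sides. Where the evidence leaves the choice open, local practice may help to decide who has the procedure, and it may also influence radiation and mastectomy. If so, region is a common cause of exposure and outcome. A matched odds ratio or hazard ratio could then depart from 1 with no effect of SLNB.

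The outcomes are not equally exposed:

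- **Aim 1 secondary outcomes (radiation, mastectomy).** These are practice decisions themselves, and no planned variable identifies regional practice.
- **Aim 1 side effects.** These are read from claims, and one of the two planned models leaves out treatment received. A path from region through treatment to side effects stays open in that model.
- **Aim 2.** Women whose primary DCIS ended in mastectomy are excluded, and an analysis stratified by radiation is planned. What remains is any regional variation in the outcomes by other routes.

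**Working it through.** **Is region handled anywhere?** Taking each device in the plan in turn:

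- Covariate list: income, education and metropolitan residence only.
- Matching distance: metropolitan county only.
- Balance check and the rule for unbalanced covariates: these act on listed factors. Registry is not listed, so it is neither checked nor added.
- Conditional logistic regression and shared frailty: both condition on the matched set. Sets can mix registries, so neither removes a registry difference.
- Strata: none is geographic.

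**How large could the effect be?** The documents give no regional rates, sample size or event counts, so there is no plan figure to reproduce. The following is illustrative, and every input is an assumption: two regions of equal size, no SLNB effect in either, and no help from the other covariates.

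Let s1, s2 be the SLNB shares and r1, r2 the outcome risks in regions 1 and 2.

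- Risk in SLNB women: pS = (s1·r1 + s2·r2) / (s1 + s2)
- Risk in controls: pC = [(1−s1)·r1 + (1−s2)·r2] / [(1−s1) + (1−s2)]
- Odds ratio: OR = [pS/(1−pS)] / [pC/(1−pC)]

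Worked case, SLNB 30% and 10%, radiation 60% and 80%:

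- pS = (0.30×0.60 + 0.10×0.80)/0.40 = 0.26/0.40 = 0.650
- pC = (0.70×0.60 + 0.90×0.80)/1.60 = 1.14/1.60 = 0.7125
- OR = (0.650/0.350)/(0.7125/0.2875) = 1.857/2.478 = 0.75

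| Outcome | SLNB, regions 1 / 2 | Risk, regions 1 / 2 | pS | pC | Spurious OR |
|---|---|---|---|---|---|
| Radiation, opposite gaps | 30% / 10% | 60% / 80% | 65.0% | 71.3% | 0.75 |
| | 35% / 10% | 55% / 80% | 60.6% | 69.5% | 0.67 |
| | 25% / 15% | 60% / 75% | 65.6% | 68.0% | 0.90 |
| | 20% / 10% | 65% / 75% | 68.3% | 70.3% | 0.91 |
| Radiation, same-direction gaps | 25% / 15% | 60% / 50% | 56.3% | 54.7% | 1.07 |
| | 30% / 10% | 70% / 40% | 62.5% | 53.1% | 1.47 |
| | 35% / 5% | 70% / 40% | 66.3% | 52.2% | 1.80 |
| Claims-coded side effect | 25% / 15% | 6% / 5% | 5.6% | 5.5% | 1.03 |
| | 30% / 10% | 10% / 5% | 8.8% | 7.2% | 1.24 |
| | 35% / 5% | 10% / 5% | 9.4% | 7.0% | 1.37 |

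If either the SLNB share or the outcome risk is equal across regions, the OR is 1.00. Within a region the two groups share the same risk by assumption, so comparing within region also returns 1.00.

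**The case against.** A reader might infer that regional differences will in fact be reported as SLNB effects. The documents do not support that. Bias needs region to predict both SLNB use and the outcome after the listed covariates. The background describes debate among experts, which fits disagreement within one area as well as between areas. Nor do the documents say that coding habits differ by area. The Methodology section describes one code set for the exposure, "We identify interventions and comparators in our study using specific international classification of Diseases, Ninth Revision, (ICD-9) codes, CPT codes and HCPCS codes", and says nothing about area differences in side-effect claims. Both objections stand: the point is about what can happen, and regional coding is only a possibility.

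The examples also set aside help that the plan may give. Income, education, metropolitan residence, MRI use and surgeon's volume may absorb part of any regional variation. For side effects, the second model adjusts for treatment. In Aim 2, regional differences in radiation receipt cannot confound within a radiation stratum. This stands too, and it is why the concern centres on radiation and mastectomy in Aim 1. The largest odds ratios need regional gaps of 20 to 30 points in both SLNB and radiation, while a side-effect risk of 6% against 5% yields only 1.03 in the mildest case.

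A second tempting inference is that exact matching on registry is required. The plan wants two controls for every SLNB patient. Smaller pools could worsen the matches on grade, size and comedonecrosis. If region predicts SLNB strongly but the outcome weakly, conditioning on it costs precision and can amplify residual confounding. That argues against a mandatory exact match. It does not argue against listing registry and checking its balance.

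**Conclusion.** The gap is real: a multi-area cohort has one metropolitan indicator as its only place variable, and no safeguard in the plan would detect or correct an imbalance by registry. Whether this produces bias, how much and in which direction cannot be settled from the documents. The odds ratios above (0.67 to 0.91 for opposite regional gaps, 1.07 to 1.80 for gaps in the same direction, 1.03 to 1.37 for a side effect) show what the assumed contrasts would do. They are not estimates for this study.

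The point matters most for radiation and mastectomy as Aim 1 outcomes, and less for claims-coded side effects. It is partly contained in Aim 2, so it should not be read as undermining the mortality or invasive-recurrence analyses as a whole. It merits a change because that change is small and best specified before analysis.

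**What to change.** - In the Methodology covariates, add SEER registry, or census region with small registries grouped.
- In the matching paragraph of Data management and statistical analysis, add registry to the factors whose balance is reported after matching.
- In the outcome models, include registry whenever it is not balanced: as a covariate in the conditional logistic models, whose strata are already the matched sets, and as a covariate or stratum in the time-to-event models.
- Allow matching within registry or region as an option where control pools are large enough, without requiring it.

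The cost is about one sentence in each of these places, some extra model parameters and a small loss of precision. No new data should be needed if the linked file holds a usable registry identifier. The plan implies this by defining residence by SEER area and taking patient data from the registries, but does not state it, so it should be confirmed.

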will include only DCIS patients who have available claims data (i.e. are enrolled in fee-for-service coverage) during the period between cancer diagnosis and the end of the follow-up (Aim 1: 9 months after DCIS diagnosis; Aim 2: either death or the last date of claims released by SEER-Medicare). Statistically, we plan to create an “unknown” category to capture those patients who had a missing value. Additionally, we will conduct sensitivity analyses regarding whether or not excluding these patients would change our findings.

To compare baseline characteristics between intervention and control groups, we will conduct standard descriptive statistics using χ^2 tests for categorical variables and t-tests for continuous variables. We will tabulate the frequencies of outcomes of interests by the intervention vs. control group. We will use multivariable analyses to test our hypotheses while controlling for unbalanced covariates, as described below.

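### Aim 2 admits only women who stay in fee-for-service Medicare until death or the last claims date, so cohort entry depends on enrolment after follow-up starts and absolute mortality is biased

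*Combined protocol and SAP*

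**What the plan says.** The inclusion rule is under Data management and statistical analysis. Only women with available claims are included, that is, those "enrolled in fee-for-service coverage) during the period between cancer diagnosis and the end of the follow-up". The end of follow-up is then defined by aim; for the long-term outcomes it is "Aim 2: either death or the last date of claims released by SEER-Medicare".

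The Methodology section sets the Aim 2 clock: "patients will be followed from 9 months after DCIS diagnosis through the latest date to which data is available in SEER-Medicare". It gives example end dates that differ by outcome: "For instance, the next SEER-Medicare linked dataset will have overall mortality through December 2015", then "breast cancer specific mortality through December 2013, and claims data (to identify treated recurrence) through December 2014". Ipsilateral invasive cancer is a registry outcome, "based on ipsilateral invasive breast cancer from SEER".

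Leaving fee-for-service is not listed as an end of follow-up, and no section censors at exit. The planned "sensitivity analyses regarding whether or not excluding these patients would change our findings" come directly after the sentence on an unknown category for missing values, so they concern women with missing values and not women who leave coverage.

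Absolute results are planned: "We will tabulate the frequencies of outcomes of interests by the intervention vs. control group", followed by Kaplan-Meier curves by group. The main Aim 2 estimates are adjusted hazard ratios, and overall survival is a benchmark for the model.

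**The concern.** Eligibility for a time-to-event analysis should be settled by time zero. Here time zero is month 9, but eligibility is settled by what happens up to many years later. Death satisfies the enrolment condition early; survival makes a woman keep meeting it. Every death among enrolled women is kept, while survivors who leave are deleted with all their person-time.

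Two effects follow. Among women still enrolled, the rule always raises the death hazard, because it removes future leavers but nobody who dies while enrolled. If frail women leave more often, those still enrolled are healthier than the full cohort, which pulls the other way. The documents do not say who leaves.

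At stake are the outcome frequencies and Kaplan-Meier curves for all-cause and breast cancer mortality. The SLNB hazard ratio and the overall-survival benchmark are also at stake if exit differs by group beyond the covariates. A distorted benchmark could fault a sound model or hide real confounding. Non-fatal outcomes are affected only so far as they are linked to death or exit.

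For some outcomes the restriction also looks unnecessary. Invasive cancer comes from the registry. Deaths have end dates separate from claims, which suggests that they need no claims either, although the source of death data is not stated. On the example dates, enrolment is required to December 2014 for a breast cancer mortality outcome that ends in December 2013.

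**Working it through.** The plan has no figure to reproduce: it states no mortality, exit rate or event count. All rates below are assumptions.

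**Inputs from the documents**
- Aim 2 diagnoses January 1998 to December 2012 (Methodology).
- Start at 9 months; claims to December 2014.
- Follow-up available therefore runs from 1.25 years (September 2013 to December 2014) to 16.25 years (October 1998 to December 2014).

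**Model.** Let d be the annual death hazard and s the annual exit hazard. A woman alive and enrolled with r years of claims left is included with probability

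P = d/(d+s) × (1 − exp(−(d+s)r)) + exp(−(d+s)r).

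A woman who dies at that moment is included with probability 1. The hazard under the rule is therefore the hazard among enrolled women divided by the mean of P, and P is below 1 whenever s > 0.

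**One case by hand.** Take d = 0.05, s = 0.03 and 10 years of follow-up.
- Die while enrolled: 0.05/0.08 × (1 − e^−0.8) = 0.344.
- Still enrolled at 10 years: e^−0.8 = 0.449.
- Kept: 0.344 + 0.449 = 0.793.
- Mortality in the retained cohort: 0.344/0.793 = 43.4%.
- True mortality: 1 − e^−0.5 = 39.3%.

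**Exit unrelated to mortality.** Averaged over the diagnosis window, with d = 5% a year (true rate 5.0 deaths per 100 person-years, true 10-year survival 60.7%):

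| Exit per year | Women dropped | Deaths per 100 person-years | Excess | 10-year survival |
|---|---|---|---|---|
| 1% | 6% | 5.2 | +5% | 59.2% |
| 3% | 18% | 5.8 | +15% | 56.4% |
| 5% | 27% | 6.3 | +26% | 53.5% |

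Breast cancer mortality, assumed at 0.2% a year and followed to December 2013, is inflated by 5%, 17% and 29%. Extending diagnoses to 2013, as Study design has it, barely changes the all-cause rates. Following deaths to December 2015 reduces the all-cause excess to about 4%, 14% and 24%.

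**Exit related to frailty** (two classes, all-cause deaths per 100 person-years):

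| Mixture (death/exit per year) | Rule | Full cohort | Bias |
|---|---|---|---|
| Half 3%/4%, half 7%/2% | 5.68 | 4.81 | +18% |
| Half 3%/2%, half 7%/4% | 5.41 | 4.81 | +12% |
| Half 3%/1%, half 7%/5% | 5.23 | 4.81 | +9% |
| 80% 2%/1%, 20% 10%/10% | 3.15 | 3.18 | −1% |
| 60% 2%/0.5%, 40% 10%/15% | 4.24 | 4.52 | −6% |

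In such mixtures the bias in 10-year survival cancels when frail women leave roughly 7 to 9 times as often (death 2% against 10% a year), or 18 to 44 times as often (3% against 7%). These ratios are indicative only.

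**SLNB ratio, true value 1.00, d = 5% a year**
- Equal exit: 1.00.
- Unexplained exit of 4% (SLNB) against 2%: 1.09 to 1.10. The reverse: 0.91 to 0.92.
- Unexplained exit of 3% against 2%: about 1.05. The reverse: about 0.96.
- Exit of 4% against 2%, with a matched covariate explaining half of the difference: 1.045; explaining 90%: 1.01.
- Exit difference fully explained by a covariate: 1.00.

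**The case against.** The strongest reply is that the aims concern associations and the main estimates are hazard ratios; absolute mortality is descriptive. With equal exit there is no material bias in the ratio, and nothing in the documents shows that exit differs by SLNB. The matching variables (age, comorbidity, income, residence, access-to-care proxies) are plausible drivers of exit. A small unexplained difference, such as 2.5% against 2% a year, moves the ratio only to 1.02. This stands: the risk to the main estimate is conditional.

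It is also fair that the direction of the absolute bias is not settled. That does not defend the rule, since following deaths regardless of enrolment returns the true rate in every scenario above.

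The wording does not say continuous enrolment, and a short protocol may simply omit censoring. But the sentence is an inclusion criterion, and its stated end points are death and the last claims date. Continuous enrolment is the natural reading; if something else is meant, the text should say so.

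Finally, the rule has a purpose: treated recurrence and lasting side effects need complete claims, and one cohort keeps the same matched sets throughout. Censoring at exit meets the first need, and a single cohort fixed at 9 months meets the second.

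**Conclusion.** The concern holds and should be fixed. That the rule selects on future enrolment is clear from the text. Its size is uncertain. Under constant hazards and exit unrelated to mortality at 1 to 5% a year, the death rate is overstated by about 5 to 26% with follow-up to December 2014. The bias remains upward if healthier women leave more or frail women leave moderately more, and can cancel or reverse if frail women leave far more. The SLNB hazard ratio is at risk only where exit differs by group beyond the matched or adjusted covariates. No section plans to report exit by group, so a reader could not judge this. Confidence is high in the mechanism and moderate in the direction and size.

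**What to change.** Four changes to the Aim 2 rules, made before the cohort is drawn:

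1. Require fee-for-service enrolment only for the comorbidity look-back and up to the 9-month landmark.
2. Censor treated recurrence and lasting side effects at the first loss of fee-for-service or the claims end date, whichever is earlier.
3. Follow mortality and registry-identified invasive cancer to each outcome's own data end date, regardless of later enrolment, after confirming that the death data do not depend on enrolment.
4. Report fee-for-service exit by SLNB group.

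The cost is one sentence in the inclusion criteria, a censoring variable from the enrolment file, outcome-specific end dates and one table. Matching is run on the larger cohort, so patients are gained.

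The downside is that claims-based outcomes then assume non-informative censoring at exit; inverse-probability-of-censoring weights could serve as a sensitivity analysis. For mortality, full follow-up is better than censoring at exit. In the two mixtures where frail women leave far more often, censoring gives 2.9 against a true 3.2, and 3.8 against 4.5, deaths per 100 person-years.

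### Year of diagnosis is a named confounder and sets Aim 2 follow-up, yet it is not a matching variable and enters the models only if a balance check flags it

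*Combined protocol and SAP*

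**What the plan says.** The Methodology section introduces its covariate list with "We plan to include the following covariates to control for confounding", and the demographic part of that list ends with "ethnicity, marital status and years of diagnosis".

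The matching paragraph in Data management and statistical analysis says the Mahalanobis distance is "calculated using age, race, residence in a metropolitan county, comorbidity, prior influenza vaccination" or a prior primary care visit, then "income, preoperative MRI use, and tumor characteristics". It adds: "Tumor characteristics include size, grade, comedonecrosis, and estrogen receptor status". Year of diagnosis is not there, and no exact match or caliper on calendar time appears elsewhere. Matching is 2:1, by "choosing the two best non-SLNB patient matches for each SLNB patient". A control claimed by several SLNB patients goes to one of them at random, and the process repeats until everyone has two.

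On analysis, the same paragraph states: "The difference in outcomes between the control and intervention groups will be estimated in a Kaplan-Meier curve". It then gives a matched-pair relative risk without tying it to an aim. The next paragraphs assign conditional logistic odds ratios to Aim 1 and time-to-event hazard ratios to Aim 2. Multivariable models take in covariates that matching has left unbalanced. Balance is judged by χ² tests on unspecified risk factors. Expected outcomes of the study mentions standardized differences, with no threshold.

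The Methodology section gives everyone in Aim 1 the same 9-month window. Aim 2 accrues from January 1998 to December 2012, starts follow-up 9 months after diagnosis, and stops (as an example of the next data release) at December 2013 for breast cancer mortality, December 2014 for claims and December 2015 for overall mortality.

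**The concern.** Other listed covariates are also unmatched (marital status, education, disability index, prior hospitalization, surgeon volume). Year stands apart for two reasons. It stands for calendar era, so practice, background treatment and coding may differ between an SLNB patient and her controls. In Aim 2 it also determines how long a woman can be observed.

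If SLNB became more common over the accrual period, SLNB patients would on average be diagnosed later than their controls and be followed for less time. An Aim 2 measure that counts who ever had the event would then make SLNB look protective with no true effect. The plan wants to use Aim 2 to find women who can forgo SLNB, so an error in that direction matters. Overall survival, the plan's benchmark for model performance, would also be harder to read, because an era difference could look like a model failure or hide one.

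**Working it through.** The plan states no sample size, event count or effect size, so there is no figure of its own to reproduce.

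**1. Potential Aim 2 follow-up (from the documents).** Follow-up = cut-off − (diagnosis date + 0.75 years).

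| Outcome (cut-off) | Diagnosed start of January 1998 | Diagnosed end of December 2012 |
|---|---|---|
| Breast cancer mortality (end 2013 = 2014.0) | 2014.0 − 1998.75 = 15.25 | 2014.0 − 2013.75 = 0.25 |
| Claims-based recurrence (2015.0) | 16.25 | 1.25 |
| Overall mortality (2016.0) | 17.25 | 2.25 |

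Members of one matched set can differ by up to 15 years. The Study design section instead runs Aim 2 accrual through 2013. A woman diagnosed at the end of 2013 would then have 2014.0 − 2014.75 = −0.75 years for breast cancer mortality, so the two windows need reconciling.

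**2. Null relative risk of ever having the event (assumed inputs).** Assumptions: equal accrual in each year 1998–2012, mid-year diagnosis, linear SLNB uptake p(y), controls drawn without regard to year, no SLNB effect, constant hazard h = 0.2% per year, cut-off 2014.0.

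- Follow-up for year y: F(y) = 2014.0 − (y + 0.5 + 0.75).
- Weights: SLNB w1(y) = p(y)/Σp; controls w0(y) = (1 − p(y))/Σ(1 − p).
- Risk: r(y) = 1 − exp(−hF(y)). RR = Σw1·r / Σw0·r, close to the ratio of mean follow-up when events are rare.
- With deaths at yearly rate μ = 3% to 8%: r(y) = [h/(h + μ)]·[1 − exp(−(h + μ)F(y))].

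| Uptake 1998 to 2012 | Mean follow-up, SLNB vs control (years) | Null RR | Null RR with deaths |
|---|---|---|---|
| 15% flat | 7.75 vs 7.75 | 1.00 | 1.00 |
| 10% to 20% | 6.86 vs 7.91 | 0.87 | 0.88–0.89 |
| 5% to 20% | 6.15 vs 7.98 | 0.77 | 0.79–0.82 |
| 5% to 30% | 5.85 vs 8.15 | 0.72 | 0.74–0.77 |
| 5% to 40% | 5.68 vs 8.35 | 0.68 | 0.70–0.74 |

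**3. Estimates that account for follow-up.** With no calendar trend in the hazard, the null rate ratio is 1.00 in every row. If the hazard falls 3% to 5% per diagnosis year (assumed), the unadjusted person-time rate ratio is 0.98 to 0.96 for uptake of 10% to 20%, and 0.94 to 0.90 for 5% to 30%.

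**4. Would the balance check catch year?** Take a χ² test over 15 diagnosis years (14 degrees of freedom, 5% level) with n1 = 200 SLNB women and n0 = 400 controls (assumed). The noncentrality is [n1·n0/(n1 + n0)]·Σ(w1 − w0)²/w̄, where w̄ = (n1·w1 + n0·w0)/(n1 + n0). It is 24.2 at 5% to 20% (power 0.92) and 38.6 at 5% to 30% (power 0.99). At 10% to 20% it is 7.8 (power 0.37). Five times the sample multiplies that by 5, to 39.2 (power 0.99).

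**5. Supply of controls under 2:1 matching on year.** Demand over supply in a year is 2p/(1 − p), which exceeds 1 once p is above one third. With uptake of 5% to 40%, p in 2010, 2011 and 2012 is 0.35, 0.375 and 0.40, so the ratios are 0.70/0.65 = 1.08, 0.75/0.625 = 1.20 and 0.80/0.60 = 1.33. With 5% to 30%, 2012 uses 0.60/0.70 = 86% of controls. A one-year window eases this: in the 40% case, 2010–2012 need 2 × (0.35 + 0.375 + 0.40) = 2.25 units, against 0.675 + 0.65 + 0.625 + 0.60 = 2.55 in 2009–2012. That is feasible but tight.

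**The case against.** The strongest reply is that the plan already has a safeguard. Matching on some covariates and regressing on the rest is a legitimate design, and the models take in whatever matching leaves unbalanced. If year were badly unbalanced, the check would usually find it (step 4) and the reported adjusted hazard ratio would include it. If year were balanced, there would be little bias. Most of this stands. A reader might infer that the Aim 2 hazard ratios ignore year; the documents do not support that. What remains is that year is not named among the factors to be checked, no threshold is given, and detection of a moderate imbalance depends on a sample size the plan does not state.

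A second reply is that Kaplan-Meier and hazard models handle unequal censoring. That is correct. One might infer that differing follow-up alone biases the curves; it does not. They are exposed only to an era trend in the hazard, and the documents give no figure for one.

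Third, the relative risk fits Aim 1 naturally, where follow-up is fixed and the follow-up bias is nil. That is also fair, but the plan does not confine it to Aim 1. Matching on preoperative MRI may absorb some era difference as well.

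Finally, the unmatched status of the other listed covariates is not in itself a fault, given the model-adjustment rule.

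**Conclusion.** The point holds in a limited form. A confounder the plan itself names is absent from the matching and is left to a conditional rule in the models. The 15-year spread in potential Aim 2 follow-up comes from the plan's own dates. The consequence differs by analysis:

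- **Aim 1:** only era differences apply.
- **Aim 2 hazard ratios:** probably protected if the imbalance is large, but this is not guaranteed in advance.
- **Kaplan-Meier curves:** no control of era beyond the matching; exposed only if the hazard has a calendar trend.
- **Matched-pair relative risk:** exposed to unequal follow-up only if it is used for Aim 2.

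The 0.87 to 0.68 range applies to that last case alone. It rests on assumed rising uptake and on control selection unrelated to year. It moves toward 1 once deaths are counted and is 1.00 with flat uptake. It should not be read as an estimate of bias in this study. The change is worth making before analysis because the variable is already planned.

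**What to change.** 1. Add year of diagnosis to the matching with a narrow window, for example within 1 year. Exact-year matching is less safe, because 2:1 matching without reuse runs out of controls in any year where SLNB use exceeds one third.
2. Include year as a forced covariate in all Aim 1 and Aim 2 models, whatever the balance check shows.
3. Report the standardized difference for year before and after matching.
4. Restrict the matched-pair relative risk to Aim 1's 9-month window, or replace it in Aim 2 with risk at a fixed horizon that handles censoring.
5. Reconcile the Aim 2 accrual end between Study design and Methodology.

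Cost: a few lines of specification and no new data. Matches on the other variables will be somewhat looser, more so if SLNB use was high in the later years. If the pool proves too thin, item 2 alone still gives prespecified control of year in the models, but not in the curves.
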